13.6.3.1. Monitoring and Management of Elevated Liver Function Tests

If a subject has a new value $>3 \times \text{ULN}$ for serum ALT and/or AST at any time after randomization, the subject will undergo a repeat confirmatory liver function test (LFT) assessment as soon as is reasonably possible but preferably within 3 to 7 days after the laboratory result is available.

Repeat LFT assessment will include the following: (1) measurement of serum ALT, AST, alkaline phosphatase, TB, direct bilirubin, and CK; prothrombin time (PT)/international normalized ratio (INR); eosinophil count; and antihepatitis A virus (total), HBsAg (confirmation of screening measurement), HCV (confirmation of screening measurement), and anticytomegalovirus/immunoglobulin M; (2) history of concomitant medication use; (3) history of exposure to environmental chemical agents, including ethanol; and (4) questioning for related symptoms. Additionally, further testing, such as liver ultrasound or magnetic resonance imaging (MRI) scanning, may be warranted to rule out additional pathology depending on clinical presentation and should be discussed with the sponsor personnel or the authorized medical monitor.

- If the repeat LFT assessment confirms that the value for serum ALT and/or AST is $>3 \times \text{ULN}$, consideration should be given to withdrawing the subject and administering no further doses of IMP. At the investigator's discretion, IMP may be interrupted and the subject may be rechallenged with the IMP after values for the LFTs have returned to baseline levels.
- If repeat LFT assessment confirms a value for serum ALT and/or AST $>5 \times \text{ULN}$, the subject will be withdrawn from IMP treatment but will be asked to continue to be followed for safety (as outlined in the protocol-specified visit schedule in [Appendix 1](#) or more frequently as determined by the investigator).
- If repeat LFT assessment confirms that the value for serum ALT and/or AST level is $>3 \times \text{ULN}$ and the subject has any of the following findings, the subject will be withdrawn from IMP treatment but will be asked to continue to be followed for safety (as outlined in the protocol-specified visit schedule in [Appendix 1](#) or more frequently as determined by the investigator):
 - TB value $>2 \times \text{ULN}$;
Note: In the case of subjects with Gilbert's disease, TB will be fractionated and the determination of $2 \times \text{ULN}$ will be based upon direct (conjugated) bilirubin.
 - INR value $>1.5 \times \text{ULN}$ (unless the subject is on a stable dose of anticoagulation medication);

- appearance or worsening of right upper abdominal discomfort, anorexia, fatigue, nausea, vomiting, fever, rash, or eosinophilia.

13.6.3.2. Monitoring and Management of Elevated Serum Creatinine Levels

If a subject experiences a decrease in eGFR to the level of 15 mL/min/1.73 m² or experiences acute renal failure, the subject will be withdrawn from IMP treatment but will be asked to continue to be followed for safety (as outlined in the protocol-specified visit schedule in [Appendix 1](#)).

13.6.3.3. Monitoring and Management of Changes in Hemoglobin Levels

If a subject experiences a decrease of >2.0 g/dL (20 g/L) from baseline in Hgb at any time after randomization, the subject will undergo a repeat confirmatory hematology testing as soon as is reasonably possible but preferably within 3 to 7 days after the laboratory test result becomes available.

Repeat hematology assessment will include the following: (1) measurement of Hgb, hematocrit (Hct), mean corpuscular hemoglobin (MCH), mean corpuscular hemoglobin concentration (MCHC), mean corpuscular volume (MCV), platelet count, reticulocyte count (percent and absolute), RBC count, and white blood cell (WBC) count with differential (absolute values only); (2) history of concomitant medication use; and (3) questioning for related symptoms. Additionally, further testing may be warranted to rule out additional pathology, depending on clinical presentation, and should be discussed with sponsor personnel or the authorized medical monitor.

- If a repeat assessment confirms a decrease >2.0 g/dL (20 g/L) from baseline in Hgb concentration, the subject should be monitored carefully during the study and return at 2-week intervals after study completion for additional Hgb measurements until the Hgb concentration returns to baseline or reaches a stable level.
- If a repeat assessment confirms a value <8 g/dL (80 g/L) for Hgb, the subject will be withdrawn from IMP treatment. The subject will return at 1-week intervals after withdrawal of IMP treatment for additional Hgb measurements until Hgb concentration returns to baseline or reaches a satisfactory conclusion.
- Subjects who are withdrawn from IMP treatment due to decreases in Hgb concentration will be asked to continue to be followed for safety (as outlined in the protocol-specified visit schedule in [Appendix 1](#)).

The investigator may choose to consult with a specialist at any time to further evaluate the cause of the alteration in hemoglobin.

13.6.3.4. Monitoring and Management of Elevated Creatine Kinase Levels

If a subject has a value $>5 \times \text{ULN}$ for serum CK at any time after randomization, the subject will undergo a repeat confirmatory assessment as soon as is reasonably possible but preferably within 3 to 7 days after the laboratory result is available. This assessment will include questioning for related symptoms.

- If the repeat CK assessment confirms an unexplained (ie, not associated with recent trauma or physically strenuous activity) CK abnormality (value $>5 \times \text{ULN}$), the subject should, if asymptomatic, receive further assessment and investigation into the cause. The presence of renal injury should be assessed, and serum CK levels should be measured approximately weekly or more frequently, if clinically indicated, until resolution. If serum CK levels continue to rise, treatment with the IMP should be discontinued.
- If symptomatic, the following steps should be completed:
 - Hold dosing with the IMP;
 - Clarify the nature, duration, and intensity of muscle symptoms;
 - Review possible predisposing factors, such as unaccustomed exercise, heavy alcohol intake, viral illness (consider performing serology);
 - Evaluate for additional diagnoses or other conditions, which can cause myopathy, including muscle tenderness (by PE), weakness, rash, measurement of serum creatinine level, and dipstick urinalysis with microscopy, if indicated;
 - Obtain clinical chemistries to assess the possibility of lactic acidosis; and
 - Follow symptoms and serum CK levels until the abnormality has resolved.

If, based on the above evaluation, an alternative explanation is suspected, consider resuming IMP once the serum CK level returns to baseline levels. If no alternative explanation exists, consider withdrawing the subject from IMP treatment.

- If the repeat assessment confirms an unexplained (ie, not associated with recent trauma or physically strenuous activity) CK abnormality (serum CK value $>10 \times \text{ULN}$) even in the absence of symptoms, the subject should be withdrawn from the study and given no further doses of IMP. In all cases, signs/symptoms and laboratory evaluations, as outlined in the bulleted point above, should be evaluated.
- If the subject is withdrawn from IMP treatment, the subject should be asked to continue to be followed for safety (as outlined in the protocol-specified visit schedule in [Appendix 1](#)).

13.6.3.5. Monitoring and Management of Potential Hypoglycemia and Metabolic Acidosis

Subjects will be educated on the signs and symptoms of hypoglycemia and will be instructed to report any signs and symptoms of hypoglycemia to the investigator.

Subjects will be reminded to report all signs and symptoms associated with hypoglycemia to the investigator at each study visit. For each occurrence of subject-reported signs and symptoms associated with hypoglycemia, the investigator will discuss these symptoms with the subject and assess whether they are attributable to hypoglycemia or to another potential cause. All investigator-confirmed occurrences of hypoglycemia will be recorded as AEs. All occurrences of signs and symptoms that are not confirmed by the investigator as attributable to hypoglycemia will be reported using the appropriate diagnosis.

Clinical laboratories will be assessed to determine any signs of anion gap metabolic acidosis. If laboratory test results are consistent with metabolic acidosis, the subject will be immediately contacted for further medical evaluation of the acidosis, and the event will be captured as an AE.

13.6.4. Total Blood Volume

The total number of venipunctures and total volume of blood collected during the study will be limited to that needed for safety assessments. The total whole blood volume collected during the study will not exceed approximately 300 mL for each subject.

13.7. Adverse and Serious Adverse Events

13.7.1. Adverse Events

13.7.1.1. Definition of Adverse Events

An AE is any untoward medical occurrence in a clinical investigation subject administered a pharmaceutical product, including control, and which does not necessarily have a causal relationship with treatment.

An AE can be:

- any unfavorable and unintended sign (including an abnormal laboratory finding), symptom, or disease temporally associated with the use of a medicinal product, whether or not considered related to the medicinal product;
- any new disease or exacerbation of an existing disease;
- any deterioration in nonprotocol-required measurements of laboratory value or other clinical test (eg, ECG or x-ray) that results in symptoms, a change in treatment, or discontinuation from IMP; or
- an adverse drug reaction (ADR; see [Section 13.7.1.2](#)).

Treatment-emergent AEs are defined as AEs that begin or worsen after the first dose of IMP.

13.7.1.2. Adverse Drug Reaction

All noxious and unintended responses to a medicinal product related to any dose should be considered an ADR. “Responses” to a medicinal product means that a causal relationship between a medicinal product and an AE is at least a reasonable possibility (ie, the relationship cannot be ruled out).

An unexpected ADR is defined as an adverse reaction, the nature or severity of which is not consistent with the applicable product information (eg, Investigator's Brochure for an unapproved investigational product or package insert/summary of product characteristics for an approved product).

13.7.1.3. Reporting of Adverse Events

All AEs that occur from the time the ICF is signed through 30 days after the last study visit should be recorded on the eCRF. Any SAE that occurs from the time the ICF is signed through 30 days after the last study visit should be reported to the sponsor per [Section 13.7.2.4](#).

Subjects should be instructed to report any AE that they experience from the time the ICF is signed through 30 days after the last dose of IMP to the investigator. Investigators should make an assessment for AEs at each visit and record the event on the appropriate eCRF.

Wherever possible, a specific disease or syndrome rather than individual associated signs and symptoms should be identified by the investigator and recorded on the eCRF. However, if an observed or reported sign or symptom is not considered a component of a specific disease or syndrome by the investigator, it should be recorded as a separate AE on the eCRF. Additionally, the condition that led to a medical or surgical procedure (eg, surgery, endoscopy, tooth extraction, transfusion) should be recorded as an AE, not the procedure.

Any medical condition already present at screening or baseline should not be reported as an AE unless the medical condition or signs or symptoms present at baseline change in severity or seriousness at any time during the study. In this case, it should be reported as an AE.

Clinically significant abnormal laboratory or other examination (eg, ECG) findings that are detected during the study or are present at baseline and significantly worsen during the study should be reported as AEs. The investigator will exercise his or her medical and scientific judgment in deciding whether an abnormal laboratory finding or other abnormal assessment is clinically significant. Significant abnormal laboratory values occurring during the clinical study will be followed until repeat tests return to normal, stabilize, or are no longer clinically significant. Any abnormal test that is determined to be an error does not require reporting as an AE.

Each AE is to be evaluated for duration, severity, seriousness, and causal relationship to the investigational drug. For each AE, the following information will be recorded:

- description of the event (eg, headache);
- date of onset;
- date of resolution (or that the event is continuing);
- action taken because of the event;
- seriousness of the event;
- severity of the event;
- outcome of the event; and

- investigator's assessment of relationship to IMP.

A cluster of signs and symptoms that results from a single cause should be reported as a single AE (eg, fever, elevated WBCs, cough, abnormal chest x-ray, etc, can all be reported as "pneumonia").

The investigator will carefully evaluate the comments of the subject and the response to treatment in order that he/she may judge the true nature and severity of the AE. The question of the relationship of AEs to IMP administration should be determined by the investigator or study physician after thorough consideration of all facts that are available.

Additional information will be collected regarding muscle-related AEs that may include, but may not necessarily be limited to, a muscle-related questionnaire, with questions regarding type of muscle-related symptoms, location of the muscle-related AE, and potential cause of the muscle-related AE.

13.7.1.4. Severity

It is the investigator's responsibility to assess the intensity (severity) of an AE. The severity of the AE will be characterized as mild, moderate, or severe according to the following definitions:

- Mild: Events are usually transient and do not interfere with the subject's daily activities.
- Moderate: Events introduce a low level of inconvenience or concern to the subject and may interfere with daily activities.
- Severe: Events interrupt the subject's usual daily activity, are incapacitating with inability to do usual activities, or significantly affect clinical status and warrant intervention and/or close follow-up.

Note: A severe AE need not be serious and an SAE need not, by definition, be severe.

13.7.1.5. Relationship

It is the investigator's responsibility to assess the relationship of the AE to both the IMP and EZE. The degree of "relatedness" of the AE to the IMP and EZE should be described using the following scale:

- Not Related: No temporal association and other etiologies are likely the cause.
- Unlikely: While cannot be definitively ruled as not related to IMP, a causal association is remote, and other etiologies are more likely to be the cause. For reporting and summarization, events assessed as "Unlikely" to be related to IMP will be considered as "Not Related" to IMP for regulatory reporting purposes.
- Possible: Temporal association, but other etiologies are likely the cause. However, involvement of the IMP cannot be excluded.
- Probable: Temporal association, other etiologies are possible but unlikely. The event may respond if the IMP is discontinued.

- Definite: Established temporal association with administration of the IMP with no other more probable cause. Typically, the event should resolve when the IMP is discontinued and recur on re-challenge.

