2. SYNOPSIS

Name of Sponsor/Company: Esperion Therapeutics, Inc.
Title of Study: A Randomized, Double-Blind, Parallel Group Study to Evaluate the Efficacy and Safety of Bempedoic Acid 180 mg + Ezetimibe 10 mg Fixed-Dose Combination Compared to Ezetimibe and Placebo in Subjects With Type 2 Diabetes and Elevated LDL-Cholesterol
Study Number: 1002FDC-058
Phase of Development: 2
Clinical Sites: Approximately 45 sites in the United States
Name of Investigational Medicinal Product (IMP): Bempedoic Acid 180 mg (BA) + Ezetimibe (EZE) 10 mg fixed-dose combination (FDC) EZE 10 mg Placebo (PBO)
Primary Objectives: The Co-primary Objectives are: 
• To assess the efficacy of FDC versus PBO on low-density-lipoprotein cholesterol (LDL-C) lowering in subjects with type 2 diabetes (T2D) treated for 12 weeks; and• To assess the efficacy of FDC versus EZE on LDL-C lowering in subjects with T2D treated for 12 weeks.
Secondary Objectives: 
• To assess the efficacy of EZE versus PBO on LDL-C lowering in subjects with T2D treated for 12 weeks;• To assess the efficacy of FDC versus PBO, FDC versus EZE, and EZE versus PBO on high-sensitivity C-reactive protein (hs-CRP), non-high-density lipoprotein cholesterol (non-HDL-C), total cholesterol (TC), apolipoprotein B (apoB), triglycerides (TG), and high-density lipoprotein cholesterol (HDL-C) in subjects with T2D treated for 12 weeks;• To assess the effect of FDC, EZE, and PBO on percent of subjects achieving LDL-C level <70 mg/dL;• To assess the effect of FDC, EZE, and PBO on percent of subjects achieving LDL-C reduction $\geq 50\%$; and• To characterize the safety and tolerability of FDC, EZE, and PBO in subjects with T2D treated for 12 weeks.
Exploratory Objectives: 
• To assess the effect of FDC versus PBO, FDC versus EZE, and EZE versus PBO on hemoglobin A_{1C} (HbA_{1C}), fasting glucose, [REDACTED] homeostatic model assessment of insulin resistance (HOMA-IR) and [REDACTED] and 2-hour postprandial glucose (PPG) in subjects with T2D treated for 12 weeks.

Study Design:

This is a Phase 2, randomized, double-blind, parallel group, multicenter study of FDC versus EZE and PBO administered for 12 weeks in subjects with T2D and elevated LDL-C. An overview of the study design is presented below.

Overview of Study Design

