10.3. Investigational Medicinal Product Accountability, Handling and Disposal

The Principal Investigator must maintain accurate records of the receipt of all study medication shipped by the sponsor/sponsor representative and the disposition of that study medication. The Principal Investigator will ensure that all IMP is stored in a secured area, under recommended storage conditions [REDACTED]

[REDACTED] in accordance with applicable regulatory requirements for investigational drugs. Access to IMP will be limited to those clinical site personnel authorized by the Investigator.

Upon completion or termination of the study, all used and unused IMP (FDC, EZE, and PBO) will be returned to the sponsor (or designee) for destruction or disposed of by the study site, per

sponsor written instruction. All IMP returns must be accompanied by the appropriate documentation.

Investigational medicinal product records or logs must comply with applicable regulations, local law, and guidelines, and should include:

- amount received/placed in storage area;
- amount currently in storage area;
- label identification or batch number;
- dates and initials of person responsible for product inventory (including entry/movement/disposition);
- date and amount dispensed to each subject, including unique subject identifier;
- data returned by subject, assessment of compliance, and relevant documentation of discrepancies;
- nonstudy disposition (eg, lost, broken, wasted); and
- amount returned to sponsor/sponsor designee.

The sponsor will provide forms to facilitate inventory control if the staff at the investigational site does not have an established quality system that meets the needs of this requirement.

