#### 5.2.9 IMP Exposure and Compliance

The length of exposure to IMP (FDC, and EZE) will be calculated as the number of days from the first dose of double-blind IMP to the last dose of double-blind IMP, regardless if the patient missed one or more doses of IMP. Length of exposure will be summarized by treatment group using descriptive statistics for the safety analysis set. The length of exposure will be calculated as first dose of PBO to the last dose of PBO in respective periods.

Confidential

Page 18 of 38

The number and percentage of patients who were compliant with taking IMP will be summarized by treatment group for the safety analysis set for the following categories 0 < 80%; >= 80%.

Overall compliance will be calculated as: 100\* (Total Number of Tablets Dispensed – Total Number of Tablets Returned) / (2\*Treatment Duration in Days). The IMP administration and compliance data, including reasons for poor compliance, if noted in CRF will be listed for each patient.

Same approach will be applied in calculating exposure and compliance for single-blinded PBO run-in period. Listing and table will be provided separately to IMP during treatment period.

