#### 5.5.1 Adverse Events (AEs)

AEs will be coded using the Medical Dictionary for Regulatory Activities (MedDRA) Version 21.0 or later and will be categorized by system organ class (SOC) and preferred term (PT). Patients with AEs that are ongoing at study completion or study withdrawal must be followed until resolution or for 30 days after the last study visit, whichever comes first. Summary tables will focus on TEAEs; however, listings will include all AEs (with non-TEAEs flagged).

Confidential

Page 21 of 38

In summary tables, TEAEs will be counted as "Not Related" if relationship to IMP was recorded as 'Not Related' or "Unlikely". Events will be counted as "Related" if relationship to IMP was recorded as 'Possible', 'Probable', 'Definite' or if relationship to IMP is missing.

The severity of the AE will be characterized as mild, moderate, or severe, to the following definitions:

- Mild: Events are usually transient and do not interfere with the subject's daily activities
- Moderate: Events introduce a low level of inconvenience or concern to the patient and may interfere with daily activities
- Severe: Events interrupt the subject's usual daily activity, are incapacitating with inability to do usual activities, or significantly affect clinical status and warrant intervention and/or close follow-up

Overviews of TEAEs will include total number of TEAEs and patient incidence of TEAE, TE SAE, related TEAE, related TE SAE, AESI, withdrew due to TEAE, Fatal TEAE. An individual TEAE summary will be presented by treatment group containing the following counts and percentages for:

- patients with TEAEs
- patients with TEAEs by PT
- patients with TEAEs by SOC, PT and maximum severity
- patients with treatment-related TEAEs
- patients with treatment related TEAEs by PT
- patients with treatment related TEAEs by SOC, PT and maximum severity
- patients with treatment-emergent serious adverse events (TE SAEs)
- patients with TE SAEs by PT
- patients with TE SAEs by SOC, PT and maximum severity
- patients with treatment-related TE SAEs
- Fatal AEs by SOC and PT
- withdrawal from IMP due to TEAEs

Patient incidence (percent of patients experiencing the AE) will be provided for overall TEAE, treatment related TEAE, TE SAE, treatment related TE SAE, and AESI.

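### The protocol asks for separate causality scores for the IMP and for ezetimibe, although ezetimibe is IMP, and the SAP uses only the IMP score, so an event attributed to ezetimibe can be tabulated as Not Related

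*Protocol*

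**What the plan says.** **What IMP means.** The protocol synopsis names the fixed-dose combination (FDC), EZE 10 mg and placebo as the investigational medicinal product. Protocol section 10.3 does the same for drug accountability, and SAP section 5.2.9 defines exposure to IMP as exposure to the FDC and EZE. Ezetimibe other than the study supply is prohibited (protocol section 9.3.1).

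**What the investigator is asked.** Protocol section 13.7.1.5 requires the investigator to "assess the relationship of the AE to both the IMP and EZE", and the next sentence again names both as targets of the scale. There are five categories. Not Related names no product; Unlikely, Possible, Probable and Definite are worded for IMP only. Possible, for example, applies where "involvement of the IMP cannot be excluded". Events scored Unlikely "will be considered as 'Not Related' to IMP for regulatory reporting purposes".

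**What is recorded.** The list of data for each adverse event in protocol section 13.7.1.3 has one causality item, the "investigator's assessment of relationship to IMP". It has no item for EZE.

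**What is analysed.** SAP section 5.5.1 counts an event as Not Related "if relationship to IMP was recorded as" Not Related or Unlikely. It counts the event as Related if the IMP score is Possible, Probable, Definite or missing. Neither document says how an EZE score would be recorded, combined with the IMP score, tabulated or listed.

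**The concern.** Asking about EZE alongside the IMP suggests to the investigator that they are different things. No background ezetimibe is allowed to which a separate score could refer, and under the blind the investigator does not know whether the subject takes EZE at all. One natural reading is that IMP means the new drug, bempedoic acid. On that reading, an investigator who suspects ezetimibe could score EZE as Possible and the IMP as Unlikely.

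The SAP would then place the event under Not Related, although the investigator has attributed it to a study product. That also sits badly with protocol section 13.7.1.2, which treats a response as an adverse drug reaction when a causal link to a medicinal product is at least a reasonable possibility.

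At stake are the summaries of treatment-related TEAEs and treatment-related serious TEAEs in SAP section 5.5.1, and the summaries of hyperglycemia and hypoglycemia by relationship in SAP section 5.5.2. Two reporting provisions also depend on the IMP score: the Unlikely rule in protocol section 13.7.1.5, and the part of section 13.7.2.4 under which an SAE after the 30-day window must be reported if the investigator considers it related to IMP. Safety and tolerability is a stated secondary objective.

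**Working it through.** No figure in the plan bears on this point, so there is none to reproduce. The check applies the SAP rule to every pair of scores.

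**Inputs.** Each score can take 6 states: the five categories of protocol section 13.7.1.5, plus missing. The classification rule is that of SAP section 5.5.1.

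**Step 1, all pairs.** 6 × 6 = 36 combinations of IMP score and EZE score.

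**Step 2, pairs in which EZE is implicated** (Possible, Probable or Definite): 3 × 6 = 18.

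**Step 3, SAP rule applied to those 18.**
- IMP score Not Related or Unlikely: 3 × 2 = 6 combinations, tabulated Not Related.
- IMP score Possible, Probable, Definite or missing: 3 × 4 = 12 combinations, tabulated Related.

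**Step 4, three rules compared over all 36 pairs.**

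| Rule for Related | Tabulated Not Related | Of these, EZE implicated |
|---|---|---|
| SAP: IMP score Possible or higher, or missing | 2 × 6 = 12 | 6 |
| Either score Possible or higher, or IMP score missing | 2 × 3 = 6 | 0 |
| Either score Possible or higher, or either missing | 2 × 2 = 4 | 0 |

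The second and third rules differ in 6 − 4 = 2 combinations: IMP scored Not Related or Unlikely, with the EZE field blank. This matters because section 13.7.1.3 lists no EZE item. If the EZE field were never filled, the third rule would make every event Related, while the second would give exactly the SAP's present result.

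These counts describe how the rules behave. They are not event rates, because nothing in the documents shows how often the two scores would disagree.

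**The case against.** The strongest reply is that the plan already works with a single score. Section 13.7.1.3 records only the relationship to IMP, four of the five categories are worded for IMP, and the SAP uses the IMP score. On this view the mention of EZE is stray wording in one section. An investigator who applies the protocol's own definition of IMP cannot score EZE as related and IMP as unrelated, and a missing IMP score counts as Related in any case. The eCRF is not among the documents, so a second field may not exist.

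Much of this stands, and it rules out three stronger readings.

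- A reader might infer that an event attributed to EZE is always tabulated as Not Related. That requires a discordant pair of scores, which the wording permits but does not compel.
- A reader might infer that an SAE attributed to EZE would miss expedited reporting. Section 13.7.2.4 requires sites to report all SAEs up to 30 days after the last dose, whatever the relationship. Section 13.7.2.5 makes the sponsor or its designee responsible for submitting suspected unexpected serious reactions, and it does not name the investigator's IMP score as the gate.
- A reader might take the two arms of three that contain EZE (112 of 168 subjects under the protocol, 156 of 234 under the SAP) as the size of the problem. Those figures count exposure. Because investigators are blinded, discordant scoring could arise in any arm, placebo included.

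The reply does not remove the contradiction. Section 13.7.1.5 is operative text and names both targets in two consecutive sentences. If a second field exists, no rule says how to use it. If it does not, the section asks for an assessment that the recorded data do not hold.

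**Conclusion.** The point holds as an inconsistency in how causality is asked for and used. The protocol requests two overlapping scores, lists one as recorded data, and the SAP analyses one. An event attributed to EZE but scored Not Related or Unlikely for IMP can be tabulated as Not Related, and the two causality-dependent reporting provisions could be affected in the same way.

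The frequency is unknown. It is zero if investigators apply the synopsis definition of IMP consistently or if no EZE score is ever given. Any percentage would be an assumption, so none is offered.

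The reach is limited. All TEAEs and serious TEAEs are tabulated irrespective of causality and all adverse events are listed, so no event disappears; only its classification could be wrong. Site reporting of SAEs within the 30-day window and the efficacy analyses are untouched. The correction is still worth making, because it costs almost nothing and closes a foreseeable route to misclassified safety data.

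**What to change.** **Preferred.** In protocol section 13.7.1.5, ask one question: relationship to blinded IMP, stated to include every component the subject may be taking (bempedoic acid, ezetimibe or placebo). This agrees with protocol section 13.7.1.3 and SAP section 5.5.1, neither of which would then need to change.

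**If two fields are already collected.** Change SAP section 5.5.1 so that an event is Related when either score is Possible, Probable or Definite, or when the IMP score is missing. State that a blank EZE field alone does not make an event Related. Add the EZE item to section 13.7.1.3, and apply the same rule to the reporting steps that depend on causality in sections 13.7.1.5 and 13.7.2.4.

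**Cost.** The preferred fix is one sentence in the protocol or the eCRF guidelines. The alternative is one derivation line in the SAP with matching text in the protocol. Either should be settled before unblinding, since it can change safety tables. The downside is that the related-event percentage may rise slightly.
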